Sustainability of Pulmonary Rehab Gains

NCT02241733

8/13/2019

Introduction. Chronic obstructive pulmonary disease (COPD) is characterized by progressive airway obstruction and limited exercise tolerance.^{1,2} A major determinant of limited exercise tolerance in COPD is the development of exercise-induced dynamic hyperinflation.³ The severity of exercise-induced dynamic hyperinflation can be reduced using several strategies⁴ including a novel breathing-retraining technique that we developed.⁵ By combining this technique with exercise-training, patients with COPD can achieve greater improvements in symptoms, functional status, and quality of life than with exercise-training alone.⁶⁻⁸

A crucial aspect of any pulmonary rehabilitation program is the maintenance of the early benefits of rehabilitation over the long-term.^{9,10} Unfortunately, in most patients those benefits significantly decrease six to twelve months after traditional rehabilitation programs have ended,^{9,11,12} and nearly disappear thereafter.¹³ The inability to maintain the benefits of traditional rehabilitation over time exposes patients to an increased risk of functional decline, exacerbations, hospitalizations, and worse quality of life.^{9,12,14,15} The few patients in whom the benefits of traditional pulmonary rehabilitation persist over time are those who achieve high self-efficacy.¹³

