General Overview of Design. The proposed study has been designed as a randomized, controlled clinical trial. After completing baseline testing, patients will be randomized to one of two groups: breathing-retraining plus exercise-training or exercise-training alone. We did not include a non-treatment group as it has been clearly demonstrated that patients randomized to a non-treatment group (no exercise-training) experience no significant improvements in exercise capacity.^{12,16}

Sample Size Calculation. Sample size calculations for the current proposal are based on two considerations. First, in our previous investigation⁶ we observed that the mean exercise endurance 6 weeks after the completion of training was 7.0 min greater with exercise plus breathing-retraining than with exercise alone. When the analysis was restricted to those patients who developed exercise-induced dynamic hyperinflation, the difference was 8.27 min. Second, due to greater gains in mastery over breathing with exercise plus breathing-retraining than with exercise alone,⁴⁷ we expect that the difference in exercise endurance between the two groups will widen over time – i.e., we expect that the breathing-retraining group will better maintain the benefits of rehabilitation than the exercise-alone group. Based on these considerations we conservatively estimate that the difference in exercise duration between the groups at 12 months will be 8.27 minutes with a pooled standard deviation of 13.7 min (effect size = .60).

This means that to achieve 85% power, 100 patients are needed (50 in each group) using two-sample t-test ($\alpha = .05$).

According to the local IRB, enrollment is the equivalent to a patient signing an informed consent. In our three latest studies,^{6,7,84} 30-46% of patients who signed the informed consent (i.e., enrollees) did not meet PFT criteria or did not qualify for other reasons. Accordingly, to have complete data on 100 patients while accounting for attrition due to disqualifying conditions, lack of exercise-induced dynamic hyperinflation, and short-term and long-term attrition, we plan to ‘enroll’ 250 patients (i.e., signed informed consent) and to ‘randomize’ 140 of them.

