Incremental-Load Treadmill Test. The purpose for this test is to determine the patient's VO_{2peak} and his/her breathing pattern during exercise. This information will be used to set the workload during the constant-load treadmill test and to set the breathing-retraining goals during exercise-training. At the start of the incremental-load test the treadmill will be set at 0% grade and at a speed of 1.8 mph. Every 30 seconds during testing, the incline will increase by 0.5%. Additionally, after minute 6 of the protocol, the treadmill's speed will increase by 0.2 mph every 3 min. With this protocol, energy demands step up by one metabolic equivalent (MET)⁹⁴ every 3 min.

Constant-Load Treadmill Test. The purpose of this test is to determine exercise duration, respiratory pattern, extent of exercise-induced dynamic hyperinflation, dyspnea and leg fatigue at randomization, after 12-weeks of training and 6 and 12 months after randomization. The speed and grade of the treadmill will be the same as the speed and grade recorded when patients reached 85% of their VO_{2peak} during the baseline incremental-load treadmill test.

Recordings During Incremental-Load and Constant-Load Tests. During all treadmill tests, cardiac activity (Leads II, V1, and V5; General Electric), SpO_2 (Nellcor Works), airflow (MedGraphics). VO_2 and VCO_2 (MedGraphics) will be monitored continuously. This setup allows us to record of minute ventilation, tidal volume, and respiration rate as well as breath-by-breath recordings of gas exchange.

As previously described,^{6,7,84} VO_{2peak} will be the highest value of VO_2 recorded between the 60 sec before and 30 sec after the incremental-load treadmill exercise test ends, when patients have reached their 'peak effort'.

Inspiratory capacity will be measured just before each exercise test, every 2 min throughout the test, at peak exercise and at 2 and 4 min into recovery.⁷ Similarly, blood pressure will be recorded every 2 min. Ratings of perceived dyspnea and exertion will be obtained using Borg's ratio scale^{49,50} during the last 30 sec of each stage of exercise. For patients experiencing exercise desaturation ($SpO_2 < 90\%$), an oxygen reservoir system (100 L Douglas bag) will be used for continuous oxygen supplementation.⁷

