The principal analysis of the primary outcome measure will compare changes in duration of exercise from baseline to end of follow-up in the constant-load treadmill test using the 2-sample t-test (two-tailed $P = .05$). The primary analysis will be based on intention-to-treat principles (i.e., all randomized patients will be included in the analysis). Multiple imputation will be used for study patients who are missing the 12-month measurement. This imputation model will be based on the baseline characteristics of the study participants. The primary analysis will be repeated, restricted to patients who complete the treatment protocol. Linear regression will be used to determine whether the observed treatment persists after adjustment for baseline covariates and measures of treatment adherence. Since several measurements will be taken on each patient, mixed-models analysis will be used to compare the changes on the constant-load treadmill test over time between the two groups. The missing data pattern will be explored to determine whether data have been informatively censored. If the data do not appear to be missing at random, an indicator variable (alone and as an interaction with slope) will be used in the model to separately estimate intercepts and slopes for the censored group and the group with complete data. At the patient level, random intercepts and slopes will be assumed. Several correlation structures will be evaluated to determine which best represents the observed correlation structure. We will also use multiple imputation to estimate the missing values in the mixed-model ANOVA as a sensitivity analysis. This will be accomplished in two ways. The first multiple imputation technique will account for the treatment group to which each study participant was randomized. We will then use a second multiple imputation model in which all missing values are imputed from a model that only includes data from the control group. This latter multiple imputation model will provide a lower bound (or conservative) estimate of the treatment differences.

Secondary Hypotheses:

H₂: ONE YEAR AFTER RANDOMIZATION, REDUCTIONS IN EXERCISE-INDUCED DYNAMIC HYPERINFLATION WILL BE GREATER IN THE BREATHING-RETRAINING GROUP THAN IN THE EXERCISE-ALONE GROUP.

Statistical analysis for H₂ will parallel that of H₁.

H₃: ONE YEAR AFTER RANDOMIZATION, IMPROVEMENTS IN THE 6-MINUTE WALK DISTANCE WILL BE GREATER IN THE BREATHING-RETRAINING GROUP THAN IN THE EXERCISE-ALONE GROUP.

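### As written, the primary imputation model leaves out randomised group, which dilutes the H1 estimate towards zero and cuts its power

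*Combined protocol and SAP*

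**What the plan says.** All of the following is in the combined protocol and SAP.

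- **Statistical Analysis, Primary Hypotheses (H1).** The principal analysis is a two-sided two-sample t-test on change in exercise duration from baseline to end of follow-up, in all randomised patients. Missing 12-month values are multiply imputed, and the only stated basis for the model is: "This imputation model will be based on the baseline characteristics of the study participants".
- **Same section, sensitivity analyses.** Further imputations are tied to the repeated-measures model: "We will also use multiple imputation to estimate the missing values in the mixed-model ANOVA as a sensitivity analysis". Randomised group appears here for the first time: "The first multiple imputation technique will account for the treatment group to which each study participant was randomized". A second version imputes from control-group data only, and the plan says of it: "This latter multiple imputation model will provide a lower bound (or conservative) estimate of the treatment differences".
- **Secondary Hypotheses.** The analyses of H2, H3 and H4 are to follow that of H1.
- **Sample Size Calculation.** The design effect is stated as "we conservatively estimate that the difference in exercise duration between the groups at 12 months will be 8.27 minutes", with SD 13.7 min, 85% power and 50 patients per group. The plan randomises 140 "to have complete data on 100 patients while accounting for attrition due to disqualifying conditions" and further losses. It gives no 12-month drop-out rate.
- **Constant-Load Treadmill Test.** The test is done at randomisation and "after 12-weeks of training and 6 and 12 months after randomization".

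**The concern.** An imputation model should contain every variable in the analysis it serves. Here the analysis compares two groups, and the model that fills in missing outcomes does not mention group. Group is not a baseline characteristic in this plan either: baseline testing is completed and eligibility settled before randomisation (General Overview of Design; Screening and Baseline Testing).

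Without group, a missing patient in either arm is drawn from a blend of both arms. The imputed part of each arm then has the same expected outcome, and the estimated difference is pulled towards zero in proportion to the missing share. Rubin's standard error does not shrink to match, so the test also becomes too strict. What is at stake is a real effect being missed in the one primary test, with H2 to H4 using the same method. False claims of benefit do not become more likely.

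**Working it through.** **Inputs from the plan.** Difference 8.27 min, SD 13.7 min, two-sided α 0.05, 50 per group with complete data, 140 randomised (70 per group).

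**Derived or assumed.** Missing share f = 40/140 = 28.6%, if all 40 patients beyond the 100 lack the 12-month test. Drop-out is random and equal by arm. Drop-outs share the completers' effect unless stated. Baseline predictors explain R² = 0 to 0.4 of outcome variance. The plan gives 13.7 as the SD of exercise duration; it is used here as the SD of change.

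**1. The plan's own figure.** Effect size = 8.27/13.7 = 0.604. Power of the t-test at 50 per group is 0.848 (noncentral t) or 0.855 (normal approximation). The 85% is reproduced.

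**2. Expected estimate without group.** With missing shares f1 (breathing-retraining) and f0 (exercise alone), pooled imputation gives

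δ × [(1 − f1) + (f1 − f0)(1 − f1)/(2 − f1 − f0)].

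With equal shares this is δ × (1 − f) = 8.27 × 100/140 = 5.91 min. Splitting the 40 losses unequally (25/15 or 30/10, either way round) gives 5.7 to 5.8 min in simulation.

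**3. Power and type I error.** The primary analysis was simulated with 70 per arm, 20 missing per arm, 20 imputations from a Bayesian normal regression, Rubin's rules with small-sample degrees of freedom, and 4,000 runs per setting. Ranges are over R² 0 to 0.4.

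| Imputation model | Mean estimate (min) | Power | Type I error |
|---|---|---|---|
| Without group | 5.91–5.92 | 0.60–0.64 | 0.009–0.020 |
| With group | 8.22–8.31 | 0.85–0.88 | 0.040–0.052 |

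Without group, Rubin's standard error averages 2.60–2.73 while the estimate's actual SD is 1.97–2.15, which explains the low type I error. Putting 5.91 min into a plain t-test at 70 per arm would give 0.72, but that ignores between-imputation variance.

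**4. By missing share.**

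| Missing per arm | 8.27 × (1 − f) (min) | Power without group (R² 0–0.4) | Power with group (R² 0.2) |
|---|---|---|---|
| 7/70 (10%) | 7.44 | 0.88–0.89 | 0.92 |
| 8/70 (11.4%) | 7.32 | 0.87 | not run |
| 9/70 (12.9%) | 7.21 | 0.84–0.86 | 0.92 |
| 10/70 (14.3%) | 7.09 | 0.83–0.84 | not run |
| 14/70 (20%) | 6.62 | 0.76–0.77 | 0.90 |
| 20/70 (28.6%) | 5.91 | 0.60–0.64 | 0.87 |

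Power without group falls below the planned 85% at roughly 13% missing.

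**5. If drop-outs do not keep the full effect.** The true all-randomised effect is 8.27 × (1 − f + f × share kept). At f = 28.6% and R² 0.2:

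| Effect kept by drop-outs | True effect (min) | Without group (min) | With group (min) |
|---|---|---|---|
| 0% | 5.91 | 5.86 | 8.25 |
| 50% | 7.09 | 5.93 | 8.25 |
| 100% | 8.27 | 5.91 | 8.31 |

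If nothing is kept, the model with group is too high by 8.27 − 5.91 = 2.36 min in expectation. At half kept, the two models miss by 1.18 min in opposite directions.

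**6. Against the plan's lower bound.** With equal drop-out and baseline data only, control-only imputation gives 5.96 min in simulation, level with the primary analysis as written. If it also uses a 6-month value (assumed correlation 0.7 with the 12-month value and full effect at 6 months), its expectation is 8.27 × [(1 − f) + f × (0.7 − R²)/(1 − R²)], which is 7.56, 7.38 and 7.09 min at R² 0, 0.2 and 0.4. The primary estimate would then lie below the stated bound.

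**The case against.** **The omission is inferred.** The plan does not say that baseline characteristics are the sole predictors, and it does use a restrictive word when limiting the later model to controls. Group may be named in the sensitivity imputation only to contrast it with the control-only version. This stands as a caveat: it may be a drafting gap. But no sentence puts group in the primary model, and a programmer following the text would leave it out.

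**The 28.6% is derived.** The 40-patient margin is for complete data, which may be stricter than attending the 12-month test. At about 10% missing, power still exceeds 85%. This stands, and the size must be read across the range.

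**Dilution is a bias only if drop-outs keep some of the effect.** This also stands. The Introduction says that "in most patients those benefits significantly decrease six to twelve months after traditional rehabilitation programs have ended", which makes loss of benefit plausible. It describes patients after traditional programmes, though, not trial drop-outs, so it does not settle the matter. It is a reason to keep the control-based analysis, not to build its assumption into the primary analysis unstated.

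**The error is conservative, and other analyses would show it.** True, but the completer repeat, adjusted regression, mixed model and group-aware imputation do not replace the primary test.

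**The lower-bound comparison is fragile.** It sets a t-test estimate against a mixed-model analysis, needs equal drop-out, and in one form rests on an assumed correlation. With 15 breathing-retraining and 25 control patients missing, control-only imputation from baseline data gives 8.27 × 55/70 = 6.50 min against about 5.83 as written. The comparison is a side remark; the main point does not depend on it.

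**Conclusion.** The concern holds: the primary imputation rule is wrong as written. Under equal random drop-out it reduces the H1 estimate by the missing fraction. At 28.6% missing, with drop-outs sharing the completers' effect, the expected estimate is about 5.9 min instead of 8.27, power about 60% instead of 85%, and type I error about 1–2% instead of 5%. At 10% missing the loss is small, and power stays above target up to roughly 13%.

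These figures rest on the plan's own effect and SD, a missing share derived from its patient counts, and an assumption about drop-outs that the documents cannot confirm. If drop-outs lose the entire effect, the written model is about right on average. The wording carries over to H2 to H4, but the plan gives no effect size or SD for them, so the magnitudes apply to H1 only.

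**What to change.** Replace the sentence on the primary imputation model with:

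> Missing 12-month durations will be imputed from a model containing randomised group (or separately by group), baseline constant-load duration and the other baseline characteristics.

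Apply the same rule to H2 to H4. If group was always intended, the sentence simply confirms it.

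Keep the control-based imputation as the conservative sensitivity analysis, because the model with group assumes that drop-outs share the effect of completers in their own arm. Add a clause saying whether the control-based model conditions on baseline data only or on interim visits too, since that determines how low its bound is. Adding the 12-week and 6-month durations to the primary model is an optional gain in precision: with group and a 6-month value, simulated power at 28.6% missing and R² 0.2 is 0.89, against 0.87 with group alone.

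The cost is one sentence and one clause in the SAP, settled before unblinded analysis. No new data are needed: group is known for every randomised patient, and the interim tests are already scheduled.

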Exacerbations. Approximately 50% of patients with moderate-severe COPD are expected to experience an exacerbation over the course of 12 months.¹⁵ Exacerbations negatively impact adherence to exercise programs and quality of life.¹⁵ Exacerbations will be monitored weekly throughout the study. Acute exacerbations are defined by changes in sputum color, volume or consistency and are accompanied by an increase in dyspnea.⁶⁰ Acute exacerbations are classified as mild (the need for increased use of inhaled bronchodilators only), moderate (the need for systemic corticosteroids and/or antibiotics), or severe (the need for hospitalization).⁶⁰ Since moderate exacerbations usually resolve in approximately two weeks,¹¹⁸

patients who experience an exacerbation within two weeks of testing will have their testing deferred until the exacerbation has resolved.

Statistical Analysis. Descriptive statistics will be used to summarize baseline characteristics of participants. Comparison of the two groups (breathing-retraining plus exercise-training and exercise-training alone) will be undertaken for all baseline variables to determine whether any imbalances on purported prognostic factors exist. T-test for two independent samples will be used for comparison of the two groups at baseline, continuous data and changes in continuous outcomes from baseline to end of treatment. The continuity-corrected chi-square test will be used to compare categorical data in the two groups at baseline and end of treatment. When this test is not appropriate due to small category frequencies, Fisher's exact test will be used. To examine the potential for response bias, baseline measurements of patients who complete and do not complete follow-up visits will be compared. This procedure will be done for the overall study sample and for each randomized group.

Primary Hypotheses:

H₁: IN PATIENTS WITH COPD, IMPROVEMENTS IN EXERCISE DURATION ON A CONSTANT-LOAD TREADMILL TEST WILL BE GREATER AFTER 12 WEEKS OF BREATHING-RETRAINING PLUS TREADMILL EXERCISE-TRAINING FOLLOWED BY A 42-WEEK ADHERENCE-INTERVENTION PROGRAM (ONE YEAR TOTAL) THAN AFTER 12 WEEKS OF TREADMILL EXERCISE-TRAINING ALONE FOLLOWED BY A 42-WEEK ADHERENCE-INTERVENTION PROGRAM (ONE YEAR TOTAL).

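### The primary imputation of 12-month treadmill time names only baseline characteristics as predictors; adding the 12-week and 6-month times and randomised group would cheaply guard against drop-out that depends on performance differently by arm.

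*Combined protocol and SAP*

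**What the plan says.** Under Statistical Analysis, Primary Hypotheses, the principal H1 analysis is a two-sample t-test on change in exercise duration from baseline to the end of follow-up, two-sided at 0.05, in all randomised patients. Patients without a 12-month measurement have it multiply imputed, and "This imputation model will be based on the baseline characteristics of the study participants". No other predictor is named for this model.

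The Constant-Load Treadmill Test section schedules the same test "at randomization, after 12-weeks of training and 6 and 12 months after randomization". A patient who leaves after the second or third of these tests has therefore already given one or two on-study values of the primary endpoint.

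The interim values are used elsewhere in the H1 text. A mixed model compares the arms over time. It has a check for informative censoring, a censoring indicator if data do not look missing at random, and two multiple-imputation sensitivity analyses: one accounts for randomised group, the other is built from control data alone. The general Statistical Analysis text also compares completers with non-completers, on baseline measurements. H2 to H4 are to be analysed in parallel with H1.

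**The concern.** Imputing month 12 from baseline characteristics treats a patient who was declining at month 6 like any completer with the same baseline. That is harmless if leaving is unrelated to what happens after randomisation. If poor performers leave, their imputed values are too good. When this happens to different degrees in the two arms, the error does not cancel and the treatment difference shifts, up or down depending on which arm is affected. The upward case matters most, because it overstates benefit.

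The plan allows for substantial loss: "we plan to ‘enroll’ 250 patients (i.e., signed informed consent) and to ‘randomize’ 140 of them", in order to have complete data on 100. It also gives some reason to doubt that missingness depends on baseline alone: about half the patients are expected to have an exacerbation during the year, and "Exacerbations negatively impact adherence to exercise programs and quality of life". The comparison of completers with non-completers uses baseline measurements, so it cannot detect drop-out that follows on-study decline.

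Leaving randomised group out of the imputation model would be a related defect, which the same sentence can cure.

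**Working it through.** **1. The plan's own figure.** Sample Size Calculation: difference 8.27 min, SD 13.7 min, two-sided alpha 0.05, power 85%. Per group, n = 2 × (1.960 + 1.036)² × (13.7/8.27)² = 2 × 8.98 × 2.744 = 49.3, so 50. The stated 100 is reproduced; exact t-test power at 50 per group is 84.8%.

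**2. Share imputed.** (140 − 100)/140 = 28.6%. This is an upper reading, because the section gives no separate post-randomisation drop-out rate. I also show 15% as an assumed lower case.

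**3. How bias arises.** Bias in an arm mean = share missing × average error of the imputed values. For example, a 1.57 min bias at 28.6% missing means imputed values that are off by 1.57/0.286 = 5.5 min on average, or 5.5/13.7 = 0.40 SD.

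**4. Simulation.** The documents give no visit correlations or drop-out rules, so these are assumptions: true difference 8.27; SD of change 13.7; adjacent-visit correlation 0.7; baseline-with-change correlation 0.2; one third of leavers go before week 12 at random; the rest leave after week 12 or month 6, with log-odds changing by 1 per SD of the last observed gain where dependence applies. There are 400,000 patients per arm, and group is in both imputation models, so only the interim values differ.

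| Drop-out depends on last gain | Baseline only, 28.6% missing | Baseline only, 15% missing | With interim times |
|---|---|---|---|
| Control arm only | 6.7 | 7.6 | 8.2–8.3 |
| Breathing-retraining arm only | 9.8 | 9.1 | 8.2–8.3 |
| Both, weaker in breathing-retraining (0.5 vs 1) | 7.6 | 7.9 | 8.2–8.3 |
| Equal in both, or random | 8.3 | 8.3 | 8.2–8.3 |

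Repeat runs agree to about 0.1 min. Biases at 28.6%: 6.7 − 8.27 = −1.57; 9.8 − 8.27 = +1.53; 7.6 − 8.27 = −0.67. As shares of 8.27 min these are 8% to 19%.

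**5. Other assumptions.** A second set-up used 70 per arm, correlations of 0.5 to 0.85, baseline-with-change correlation 0.3, and all drop-out after month 6 (log-odds 1 per SD of 6-month change). At 28.6% missing the baseline-only bias was −1.3 to −2.6 min (control only), +1.3 to +2.5 (breathing-retraining only), −0.4 to −0.8 (same rule in both) and about 0 (random). Opposite rules in the two arms gave +2.8 to +5.0. With interim times and group in the model, bias was within ±0.07 throughout.

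**6. Precision.** Under random drop-out at 70 per arm, adding interim times multiplied the variance of the 12-month arm mean by 0.92 (one third leaving early) or 0.88 (none early). That is an 8–12% saving, or about 4–6% of the standard error (1 − √0.92 = 0.04; 1 − √0.88 = 0.06).

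**7. Limit of the remedy.** When leaving depended on the next, unobserved gain, adding interim times removed only about a third to 40% of the bias.

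**8. If group is also left out.** Under random drop-out the expected difference shrinks to about 8.27 × (1 − 0.286) = 5.9 min, a loss of about 2.4 min.

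**The case against.** Several stronger readings are tempting, and the documents do not support them.

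- *Any drop-out related to how patients are doing biases the result.* It does not. With equal dependence in both arms the bias is zero or small. Nothing in the documents says that drop-out will work differently by arm, and both arms have the same testing schedule and follow-up contacts.
- *The protocol itself says exacerbations drive patients out.* The Exacerbations section says they reduce adherence to exercise. It defers testing until an exacerbation near a test has resolved, and a non-adherent patient can still be tested under intention-to-treat. The section gives grounds for caution; it does not predict drop-out.
- *The plan forbids use of interim values.* The sentence does not say that baseline characteristics are the only predictors. They are simply the only ones named.
- *The interim data are thrown away.* The mixed model uses them, and its censoring indicator and two sensitivity imputations are real safeguards.
- *Adding interim times removes the bias.* That holds when leaving depends on values already observed. It does not hold for early leavers whose drop-out is informative, or for decline between visits.

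On scale, the standard error of the difference at 50 per arm is 13.7 × √(2/50) = 2.74 min, so biases of 0.67 to 1.57 min are 0.24 to 0.57 standard errors.

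All of this stands, and it limits the point without removing it. The safeguards belong to the supportive analysis and do not alter the t-test that decides H1. The plan does not say which result prevails if the two disagree.

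**Conclusion.** The point holds in a conditional form, as a cheap improvement. The imputation for the principal analysis names neither the interim treadmill times nor randomised group. If drop-out depends on performance differently by arm, the difference can be off by roughly 0.7 to 1.6 min either way, with up to 28.6% missing, adjacent-visit correlation 0.7 and group in the model. The bias is about half that at 15% missing. The second set-up, in which every leaver has a 6-month value and leaving depends on it, gives larger biases for one-arm dependence. Drop-out by opposite rules in the two arms is an extreme for which the documents give no support. The modest precision loss is the only consequence that does not need differential drop-out. The sample size is unaffected.

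**What to change.** Replace the sentence on the primary imputation model with:

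> Missing 12-month constant-load duration will be imputed separately by randomised group (or with group in the model) from baseline characteristics, baseline duration and the observed 12-week and 6-month durations, with exacerbations recorded before drop-out as auxiliary variables.

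Do the same for H2, which is measured during the same treadmill test. Do it for H3 and H4 wherever interim values are collected: the documents give 12-week and 6-month timing for the treadmill test, but not for the 6-minute walk or the mastery score. In the response-bias check, compare completers and non-completers on last observed duration as well as on baseline.

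The cost is a few sentences and a slightly larger imputation model. The treadmill times and exacerbations are already collected, so no visit is added. Keep the mixed model and the planned sensitivity imputations, because patients who leave before week 12 have no interim treadmill value and drop-out driven by unobserved values is only partly corrected.

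### Control-only imputation is called a lower bound on the treatment difference, but it is conservative only relative to arm-specific imputation, and the drop-out-indicator model depends on a missing-at-random judgement that the data cannot settle

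*Combined protocol and SAP*

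**What the plan says.** The points below are in the Statistical Analysis section under H1; the plan states that H2 to H4 will be analysed in parallel.

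- The supporting mixed model compares the groups on the constant-load test over time. After the missing-data pattern has been explored, "If the data do not appear to be missing at random, an indicator variable (alone and as an interaction with slope) will be used". No criterion for that judgement is given.
- The plan will also "use multiple imputation to estimate the missing values in the mixed-model ANOVA as a sensitivity analysis", in two ways. The first model takes account of randomized group. In the second, "all missing values are imputed from a model that only includes data from the control group". Both are run whatever the data look like.
- The second is described without any condition: "This latter multiple imputation model will provide a lower bound (or conservative) estimate of the treatment differences".
- The constant-load test is done at randomization and again "after 12-weeks of training and 6 and 12 months after randomization", so a patient without a 12-month result may have earlier post-baseline results. The plan does not say whether these enter the control-only model.

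No planned analysis sets drop-outs below controls by a stated amount, or shows where the conclusion would change.

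**The concern.** Control-only imputation assumes that breathing-arm patients with missing results resemble observed controls. That is one particular not-at-random assumption. Drop-outs may do worse than observed controls, and if they do so more in one arm, or more patients leave one arm, the true difference can lie on either side of the estimate. A result that holds up under this analysis has survived one assumption, with nothing to show how far drop-outs could depart from it. The label invites a reader to treat it as the worst case.

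The condition on the indicator model is a separate weakness. Observed data can show that values are not missing completely at random. They cannot separate missing at random from missing not at random. The comparison of baseline measurements between completers and non-completers cannot settle this either. Whether the model is run therefore rests on an unverifiable, data-dependent judgement.

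**Working it through.** **Inputs.** The Sample Size Calculation section assumes that "the difference in exercise duration between the groups at 12 months will be 8.27 minutes with a pooled standard deviation of 13.7 min", and randomizes 140 "to have complete data on 100 patients while accounting for attrition due to disqualifying conditions". The label under review has no figure of its own. The sample size does reproduce: 8.27/13.7 = 0.60 gives 50 per group, with power 85.5% by the normal approximation and 84.8% by the noncentral t.

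**Assumed.** 70 per arm, and 20 missing per arm as the most that 140 and 100 imply (40/140 = 28.6%). The plan states no post-randomization rate, and its attrition list includes losses before randomization, so 15 and 10 missing are shown too. Completers differ by Δ = 8.27 min. The mixed model is approximated by the 12-month two-group comparison.

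**Algebra.** Set the control completers' mean to 0 and the breathing-arm completers' mean to Δ. Let f be the fraction missing and d the shortfall of drop-outs below the control-imputed mean, in the breathing (T) and control (C) arms. If earlier tests are not used:

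- control-only estimate = (1 − fT) × Δ
- true difference = (1 − fT) × Δ − fT × dT + fC × dC

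The true difference is below the estimate exactly when fT × dT > fC × dC.

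**Results.** The last three columns assume a shift in the breathing arm only. The crossing is where P reaches .05, from simulated multiple imputation with Rubin's rules.

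| Missing per arm | Control-only estimate | True difference, dT = 5, dC = 0 | Crossing, below control mean | Same, below breathing-arm completers |
|---|---|---|---|---|
| 20 | 8.27 × 50/70 = 5.91 (P about .03) | 5.91 − 1.43 = 4.48 | about 2 min | about 10 min |
| 15 | 8.27 × 55/70 = 6.50 (P about .014) | 6.50 − 1.07 = 5.43 | about 6 min | about 14 min |
| 10 | 8.27 × 60/70 = 7.09 (P about .006) | 7.09 − 0.71 ≈ 6.37 | about 13 min | about 21 min |

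Other cases:

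- **Equal drop-out (20 per arm), equal shortfall:** the two terms cancel and 5.91 is correct. Equal shifts of 5 and 10 min leave P below .05 (about .034 and .043).
- **20 missing per arm, shortfall 5 in breathing and 10 in control:** 5.91 − 1.43 + 2.86 = 7.34, above the estimate.
- **Unequal drop-out, 26 breathing and 14 control, shortfall 5 in both:** estimate 8.27 × 44/70 = 5.20; true difference 5.20 − 1.86 + 1.00 = 4.34. With 14 and 26, estimate 6.62 and true difference 7.47.
- **Observed effect the other way, Δ = −4.0, 20 missing per arm:** control-only gives −4.0 × 50/70 = −2.86, above the arm-specific −4.0. So even *conservative* depends on the sign of the observed effect.

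**If drop-outs' earlier tests enter the model.** Breathing-arm drop-outs then carry forward part of any earlier gain:

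estimate = (1 − fT) × Δ + fT × slope × earlier difference × share of drop-outs with an earlier test

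The earlier difference is assumed to be 8.27 min, the slope 0.3 to 0.9, and the share one half to all. With 20 missing per arm:

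- low end: 5.91 + 0.286 × 0.3 × 8.27 × 0.5 = 5.91 + 0.35 = 6.26
- high end: 5.91 + 0.286 × 0.9 × 8.27 × 1 = 5.91 + 2.13 ≈ 8.03

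If drop-outs in both arms end at the same level, the true difference is 5.91. The supposed bound is then too high with no difference between arms in where drop-outs end. This is illustrative only.

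The 8.27 figure is used because this trial requires a fall in inspiratory capacity during exercise. The other available figure, that "the mean exercise endurance 6 weeks after the completion of training was 7.0 min greater with exercise plus breathing-retraining than with exercise alone", covers all patients in the previous study. Neither was measured at this trial's test times.

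**The case against.** The strongest reply is that this is largely wording. The sentence follows directly on two imputations, adds *or conservative* in brackets, and can be read as saying only that the second gives a smaller estimate than the first. It concerns a sensitivity analysis of a supporting model, and the plan nowhere says a result will be reported as surviving its worst case. This stands, and it is why the point is minor. But the sentence states no condition, and a bound is a stronger property than being smaller than one alternative.

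The second reply is that the lower true values need a shortfall larger in the breathing arm, or more drop-out there. The documents predict neither. Both arms receive the same exercise prescription, pedometer, calls and booster visits, with breathing-retraining added. The reverse pattern makes the estimate too low. This also stands: the cases above show what the label fails to exclude, not what is expected.

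Third, existing coverage is real. Both imputations are unconditional, one of them is already a not-at-random analysis, and the indicator model, if run, lets drop-outs follow a worse course. What remains is that its use is conditional and that no stated shift is examined.

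A reader might infer from the 2 min crossing that a positive result would be fragile. The documents do not support that. It belongs to the highest missingness considered, with a shift in one arm only. Even there, breathing-arm drop-outs would have to end about 10 min below their own arm's completers, more than the whole assumed effect.

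**Conclusion.** The label is wrong as written. Control-only imputation is conservative relative to arm-specific imputation when the observed effect favours breathing-retraining; it does not bound the true difference. Under the stated assumptions, a 5 min shortfall confined to breathing-arm drop-outs puts the true difference 0.7 to 1.4 min below the estimate. If earlier tests are used, the estimate could be about 0.4 to 2.1 min too high even when drop-outs in both arms end at the same level. That second range rests on several stacked assumptions and should not be cited as an expected bias.

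The condition on the indicator model cannot be verified from observed data.

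A reader might go further and infer that the primary analysis is compromised or that the plan has no not-at-random analysis. Neither follows: the primary test, alpha and sample size are untouched, and the control-only imputation is such an analysis. Severity is minor, because the point limits what may be claimed from a sensitivity analysis.

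**What to change.** 1. Replace the lower-bound label with: *control-based imputation, conservative relative to arm-specific imputation when the observed effect favours breathing-retraining*. State whether drop-outs' own 12-week and 6-month tests enter that model.
2. Run the drop-out-indicator model as a sensitivity analysis however the data appear.
3. Add a prespecified delta-adjusted tipping-point table, with the shift varied separately by arm and equal shifts included. The trial team should justify the range; the documents give no basis for a particular one.

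The cost is wording, a little more code and one table. With few drop-outs, some perhaps without any post-baseline test, pattern-specific estimates will be imprecise and should be reported as such.
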